## ***Template Instructions***

### ***Sections that do not apply:***

- *In several sections, the addition of checkboxes for **Not Applicable** have been added to the template as responses.*
  - *If an N/A checkbox is present, select the appropriate justification from the list.*
  - *If an N/A checkbox is not present, or if none of the existing checkboxes apply to your study, you must write in your own justification.*
- *In addition:*
  - *For research where the only study procedures are records/chart review: Sections 19, 20, 22, 23, 24, 25, 31, and 32 do not apply.*
  - *For exempt research: Sections 31 and 32 do not apply.*

### ***Studies with multiple participant groups:***

- *If this study involves multiple participant groups (e.g. parents and children), provide information in applicable sections for each participant group. Clearly label responses when they differ. For example:*

#### **Response Example**

Intervention Group:

Control Group:

### ***Formatting:***

- *Do not remove template instructions or section headings when they do not apply to your study.*

*If you are pasting information from other documents using the “Merge Formatting” Paste option will maintain the formatting of the response boxes.*

### ***Amendments:***

- *When making modifications or revisions to this and other documents, use the **Track Changes** function in Microsoft Word.*
- *Update the version date or number **on Page 3.***

**REVISION HISTORY**

Revision #	Version Date	Summary of Changes	Consent Change?
1	1/29/20	Adding 2 MRI scans	yes
2	3/30/23	1) Adding 15 patients. 2) All new patients will receive medium-dose lithium therapy. 3) The Week-12 study visit will be eliminated. 4) There will be some changes to the blood-based biomarkers assessed.	yes
3	5/30/23	Added language required by CTSC regarding MRI data storage and transmission.	no
4	11/30/23	Parking fee reimbursement for subjects	no

**FUNDING:**

*Indicate any funding for this proposal. This should match the Funding Sources page in Click IRB.*

Response: UB Clinical and Translational Science Award (CTSA) under UL1TR001412.

**GRANT APPLICABILITY:**

*Indicate whether this protocol is funded by a grant (e.g. NIH, foundation grant).  
For a grant with multiple aims, indicate which aims are covered by this research proposal.*

*NOTE: This question does not apply to studies funded by a sponsor contract.*

 *Include a copy of the grant proposal with your submission.*

*Response: This study is being funded by a UB Clinical and Translational Science Award (CTSA) under UL1TR001412.*

### 1.0 Study Summary

Study Title	Repurposing lithium as a disease-modifying therapy in Parkinson's disease: A Phase I trial
Study Design	Open-label
Primary Objective	Determine if medium-dose lithium aspartate therapy in an additional 15 patients is associated with similar improvements in blood-based therapeutic targets and MRI-based biomarkers as observed in the previous four patients receiving this dosage.
Secondary Objective(s)	Determine the tolerability of medium-dose lithium aspartate when titrated to a dosage of 30-45mg/day.
Research Intervention(s)/ Investigational Agent(s)	Lithium aspartate.
IND/IDE #	IND exempt (#135530)
Study Population	Parkinson's disease (PD)
Sample Size	15
Study Duration for individual participants	25-27 weeks
Study Specific Abbreviations/ Definitions	Parkinson's disease (PD), Over-the-counter (OTC)

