#### Preliminary Data:

Based on the above background, we conducted an open-label, randomized, pilot trial assessing the effects of three lithium dosages for six months on both blood-based therapeutic targets and MRI-based disease-progression biomarkers among 16 PD patients. This study was funded by the Buffalo Blue Sky Coin program. Because of the limited amount of funding, MRI scans could only be assessed on seven patients. Nevertheless, this pilot study's results showed the lithium aspartate dosage of 45mg/day to robustly engage the therapeutic targets of PBMC Nurr1 and SOD-1 and also to be associated with longitudinal *reductions* in pSN, DMN-T and nbM FW.

In this pilot trial, 16 PD patients were randomized to "low-dose" or "medium-dose" lithium aspartate (15mg or 45mg/day, respectively) or "high-dose" lithium carbonate therapy titrated to a target trough serum lithium level of 0.4-0.5mmol/L for 24-weeks (clinicaltrials.gov: NCT04273932). Three additional PD patients

served as controls and did not receive lithium for 24-weeks. Among the six patients receiving medium-dose lithium, two withdrew due to side effects of sedation and brain fog. No other patients reported side effects. One of the patients who withdrew subsequently resumed lithium aspartate at 30mg/day and reported no side effects with a steady-state trough serum lithium level <0.1mmol/L.

[figure not shown]
Results showed PBMC Nurr1 mRNA levels increased by 420%, 679%, 93% and 139% in the high, medium and low-dose lithium and control groups, respectively, after 24-weeks. Because an *in vitro* study showed that a 180% increase in Nurr1 protected neuronal cells from rotenone-induced death, we defined a “Nurr1 responder” as having a 6-month Nurr1 increase of >200%. With this definition, the Nurr1 responder rates for each lithium dosage and controls were 20%, 75%, 20% and 0%, respectively. Serum lithium levels at six months were 1282, 828, 195 and 0.73µg/L, respectively. In addition, PBMC SOD-1 mRNA increased by 18%, 127%, -1% and 8%, respectively, and by 125% and -21% in Nurr1 responders and non-responders, respectively, after six months. Lithium treatment did not appear to affect PBMC pS9/total glycogen synthase kinase (GSK-3B) ratio levels or plasma alpha-synuclein levels in a dose-response manner.

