**Table 1: Mean FW Longitudinal Changes from Pilot Lithium/PD Trial, UF and PPMI Longitudinal Cohorts**

	Mean Change in DMN-T FW	Mean Change in nbM FW	Mean Change in pSN FW
High-Dose Lithium (24-Week Changes)	-0.0117 (n=2)	-0.0140 (n=2)	0.0198 (n=2)
Medium-Dose Lithium (24-Week Changes)	-0.0098 (n=2)	-0.0416 (n=2)	-0.0307 (n=2)
Low-Dose Lithium (24-Week Changes)	0.0123 (n=2)	-0.0306 (n=2)	0.0787 (n=2)
PD from UF (1-Year Changes)	---	---	0.038  (n=25)
Aged-Matched HCs from UF (1-Year Changes)	---	---	0.001  (n=19)

PD from PPMI (1-Year Changes)	0.0100 ± 0.030  (n=130)	0.0025 ± 0.041  (n=130)	0.0180 ± 0.055  (n=103)
Aged-Matched HCs from PPMI (1-Year Changes)	0.0005 ± 0.024  (n=58)	-0.0085 ± 0.034  (n=58)	0.0070 ± 0.030  (n=49)

FW: free water, PD: Parkinson's disease, UF: University of Florida, PPMI: Parkinson's Progression Markers Initiative, DMN-T: dorsomedial nucleus of the thalamus, nbM: nucleus basalis of Meynert, pSN: posterior substantia nigra, HC: healthy control.

In summary, this pilot study showed medium-dose lithium therapy to have the most robust therapeutic target engagement of PBMC Nurr1 and SOD-1 mRNA expression and the most robust improvements in known MRI disease-progression biomarkers but to also have a high rate of side effects. Also, these results stem from only four and two patients receiving this lithium dosage with blood-based and MRI biomarker data, respectively. If similar results were found in a larger number of PD patients treated with medium-dose lithium therapy in a manner to improve clinical tolerability, such preliminary data would form a strong grant application to the Michael J Fox Foundation and/or the NIH to support a larger RCT.

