## 5.0 Study Design\*

*5.1 Describe and explain the study design (e.g. case-control, cross-sectional, ethnographic, experimental, interventional, longitudinal, observational).*

Response:

We will enroll 15 additional PD patients within five months. Eligible patients will have PD for <4 years diagnosed by a movement disorder specialist (Drs. [name] or [name]), be 45-80 years old, have normal thyroid and renal function at the screening visit, have no previous exposure to lithium therapy, have no history of brain surgery, have no hx of brain imaging findings suggesting another neurological condition besides PD, have no use of tobacco or THC products for >1 year, have stable PD medications for >30 days without current need for adjustments in the investigator's opinion, and have stable psychiatric and diuretic medications for >60 days with no anticipated need for changes for at least 24 weeks.

All patients will receive medium-dose lithium aspartate therapy (30-45mg/day) for 24 weeks ensuring that the study will be completed within 12 months. The following dose titration will be used in order to minimize side effects: 10mg bid x 1 week, then 15mg bid x 1 week, then 20mg bid x 2 weeks, then 20mg qAM and 25mg qhs thereafter. Patients will be contacted weekly over the first 4-6 weeks to assess for side effects that are likely to be due to lithium, such as sedation, dizziness or confusion. If side effects occur and are bothersome to the patient, the dose will be decreased incrementally to a minimum of 30mg/day. Such a design will enable identification of the maximum tolerated dose for study in a future trial and maximize the number of patients receiving the most promising dose (45mg/day) identified in the previous pilot clinical trial. Blood-based biomarkers and MRIs will be assessed at baseline and 24 weeks.

The primary blood-based biomarker outcome measure will be change in PBMC Nurr1 mRNA expression from baseline to 24 weeks, which will be compared with the data from the three control PD patients from the pilot study using ANCOVA. PBMC mRNA expression will be assessed by quantitative real-time PCR using TaqMan probes to match the pilot study's methodology. Based on the

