22% standard deviation among the three control patients and the 540% treatment effect size for the primary outcome from the pilot study results, only two patients would be needed to detect a difference with 95% power at a 2-tailed alpha of 0.05. Secondary outcome measures will include 24-week changes in PBMC SOD-1 expression, PBMC pS9/total glycogen synthase kinase-3B (GSK-3B) and pThr308, pS473 and t-Akt and plasma interleukin-6 (IL-6) levels. Blood-based biomarkers will be assessed by [name]. Statistical analyses will be performed by [name].

The primary MRI outcomes will be 24-week MRI changes in DMN-T, nbM and pSN FW. Using ANCOVA, these outcomes will be compared with the known natural history of such changes in PD derived from the UF and PPMI longitudinal cohorts summarized in Table 1. In addition, secondary comparisons will be made between changes in these lithium-treated patients and age-matched and disease-duration-matched PD subsets from PPMI.

Exploratory clinical outcomes will include changes in Movement Disorder Society-Unified Parkinson's Disease Rating Scale (MDS-UPDRS) Part III (Motor Examination) with subjects in the "on" state, Montreal Cognitive Assessment (MoCA), Parkinson's Anxiety Scale, Geriatric Depression Scale-15, Fatigue Severity Scale, Insomnia Severity Index and Parkinson's Disease Questionnaire-8. Adverse events and medication compliance will be assessed at a three month phone call. Trough serum lithium and safety labs including HgA1C will be assessed at each visit. Because both baseline and on-treatment lithium levels will mostly be below the level of detection using conventional clinical laboratory services (i.e. Kaleida or Quest), these assays will be performed by the UB Chemistry Instrument Center under the direction of [name]. A protocol was developed by Drs. [name] and [name] for these assays for the pilot study that provided reliable results able to detect baseline lithium levels in all patients prior to initiation of lithium therapy.

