**Statistical analyses:**

All statistical analyses of outcomes at each time point will be performed using identical methodologies. The statistical assessment of each considered outcome will be based on a standard analysis of variance (ANOVA) model. In this case, each outcome will be fit as a function of randomized group assignment, baseline cognition, and the interaction between group assignment and baseline cognition. Rather than utilizing the null distribution associated with the classic tests for treatment differences within the ANOVA framework which is dependent on the validity of distributional assumptions, an exact permutation testing approach will be utilized. The randomization mechanism at work is a crucial component in this study in that it will be used to create the randomization distribution by which statistical significance will be determined. Reported p-values will be obtained from the permutation distributions of the test statistics based on 10,000 Monte Carlo simulations. All possible pairwise comparisons will be made between the three treatment groups in conjunction with a Bonferroni adjustment for multiple comparisons performed at a 0.05 family-wise error rate. All statistical tests will be two-sided. In addition, since the comparability of treatment groups may be questioned due to chance imbalance in confounding variables, covariates will be added to the above models as a series of secondary analyses. The interaction of patient covariates and randomized assignment will be examined so to assist in the identification of patient subgroups of interest. All adverse events will be recorded during the study period and then tabulated at the end of the study along with the results of the physical exams. All available data from subjects who fail to complete this study will be included in the safety summaries. The probability of an adverse event will be estimated for each treatment group along with the 95% exact confidence interval based on the method of Clopper and Pearson. All analyses will be carried out using SAS version 9.4 (or higher) statistical software (Cary, NC).

*19.2 If applicable, provide a power analysis.*

*NOTE: This may not apply to certain types of studies, including chart/records reviews, survey studies, or observational studies. This question is asked to elicit*

*whether the investigator has an adequate sample size to achieve the study objectives and justify a conclusion.*

Response: N/A

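### The primary objective asks for improvement similar to four pilot patients, but only two of them had MRI data and no planned analysis estimates or tests that similarity

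*Combined protocol and SAP*

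**What the plan says.** - **Objective.** Sections 1.0 and 2.1 ask whether 15 further patients show improvements in blood targets and MRI biomarkers similar to those "as observed in the previous four patients receiving this dosage".
- **Pilot basis.** The summary after Table 1 in Section 4.1 says "these results stem from only four and two patients receiving this lithium dosage with blood-based and MRI biomarker data, respectively". Table 1 shows n=2 for the medium dose in all three brain regions.
- **Hypothesis.** Section 2.2 states a different question: whether lithium engages one or more blood targets and MRI biomarkers.
- **Primary blood analysis.** Section 5.1 takes the 24-week change in PBMC Nurr1 mRNA, "which will be compared with the data from the three control PD patients from the pilot study using ANCOVA".
- **Primary MRI analysis.** In Section 5.1, for DMN-T, nbM and pSN free water, "these outcomes will be compared with the known natural history of such changes in PD derived from the UF and PPMI longitudinal cohorts". Secondary comparisons use "age-matched and disease-duration-matched PD subsets from PPMI".
- **Section 19.1.** The models use randomized group assignment with permutation tests, and "All possible pairwise comparisons will be made between the three treatment groups". In the current study every patient receives the same regimen (Section 5.1). Section 19.2 gives the power analysis as not applicable.

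**The concern.** The objective, the hypothesis and the analyses ask three different questions. The objective concerns likeness to a named set of treated patients. The Section 5.1 tests concern difference from untreated patients. The Section 19.1 tests concern differences among randomized arms that this cohort does not have. If the plan is followed as written, either the primary objective goes unanswered or similarity is read off a p-value against a different comparator.

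This matters because Section 4.1 says that similar results would form the basis of a grant application for a larger randomized trial. A result well short of the pilot's could still be significant against untreated references and be presented as replication. For MRI, the wording of the objective also suggests a pilot base twice as large as the one that exists.

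**Working it through.** **1. What each planned comparison addresses**

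| Source | New cohort compared with | Addresses similarity to pilot medium-dose patients? |
|---|---|---|
| 5.1, Nurr1 | 3 untreated pilot controls | No |
| 5.1, free water | UF and PPMI natural history | No |
| 5.1, free water (secondary) | Matched PPMI PD subsets | No |
| 19.1 | Pairwise, three randomized groups | No, and cannot be run with one arm |

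No section sets a similarity margin or plans an interval against the pilot medium-dose patients.

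**2. The plan's own sample-size figure**

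Section 4.1 reports "Results showed PBMC Nurr1 mRNA levels increased by 420%, 679%, 93% and 139% in the high, medium and low-dose lithium and control groups", so the effect in Section 5.1 is 679 - 139 = 540 points. With the control SD of 22, two-sided alpha 0.05 and 95% power, a two-sample t calculation needs 2 per group (the normal approximation gives 1). The stated two patients is reproduced. It is the number needed to show a difference from untreated controls and says nothing about similarity.

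**3. Can a much smaller effect be significant against untreated references?**

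Two-sample t-tests, two-sided alpha 0.05, are used here as an approximation to the planned ANCOVA.

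- Nurr1, 15 treated vs 3 controls, true effect one quarter of the pilot's (540/4 = 135 points): power is above 99% at SD 22, 98% at SD 50 and 52% at SD 100. SDs of 50 and 100 are assumed; at SD 200 power falls to 17%.
- pSN free water, 15 treated with no mean change vs the UF mean of +0.038 (n=25): power is about 54% at SD 0.055. The UF SD is not given, so the PPMI value is assumed. The pilot signal was a reduction, so zero change would not reproduce it.

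**4. How precise would a direct new-versus-pilot comparison be?**

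95% CI half-width = t(0.975, n1+n2-2) × SD × sqrt(1/n1 + 1/n2).

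MRI, 15 vs 2: t(15 df) = 2.131 and sqrt(1/15 + 1/2) = 0.753. The only free-water SDs in the documents are the one-year PPMI values in Table 1. They are assumed here for 24-week treated changes and then halved to show the range. For pSN: 2.131 × 0.055 × 0.753 = 0.088.

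| Region | Pilot change (n=2) | PPMI PD SD | Half-width | Half-width at half SD |
|---|---|---|---|---|
| pSN | -0.0307 | 0.055 | 0.088 (2.9 × pilot change) | 0.044 (1.4 ×) |
| nbM | -0.0416 | 0.041 | 0.066 (1.6 ×) | 0.033 (0.8 ×) |
| DMN-T | -0.0098 | 0.030 | 0.048 (4.9 ×) | 0.024 (2.5 ×) |

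Nurr1, 15 vs 4: t(17 df) = 2.110 and sqrt(1/15 + 1/4) = 0.563.

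| Assumed treated SD (points) | Half-width (points) | Share of pilot mean 679 |
|---|---|---|
| 22 (the control SD) | 26 | 4% |
| 100 | 119 | 17% |
| 300 | 356 | 52% |
| 500 | 594 | 87% |

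**5. Responder rate**

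The pilot text says "the Nurr1 responder rates for each lithium dosage and controls were 20%, 75%, 20% and 0%, respectively". For the medium dose, 75% of four patients is 3/4, with a Clopper-Pearson 95% CI of 19% to 99%. That is a wide target to be similar to.

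**The case against.** The best defence is that similar improvements means replication in the ordinary sense: do new patients also improve? The pilot judged free water against natural history and the Nurr1 effect against controls, and Section 5.1 uses the same yardsticks. Section 2.2 asks about target engagement, which Section 5.1 tests. Section 19.1 also plans means, SDs and ranges, and the pilot means are printed, so a reader could set the two side by side. This stands in part: Section 5.1 gives an indirect answer to a same-direction question. But the plan never says that this is the intended reading, and step 3 shows that passing the 5.1 tests does not require an effect near the pilot's.

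Three stronger readings are tempting, and the documents do not support them.

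- **That every planned test is against untreated patients.** This is true of the Section 5.1 biomarker comparisons. Section 19.1 plans comparisons among three treatment groups. Those do not fit a one-arm cohort, but they are in the plan.
- **That the protocol misstates or hides the pilot numbers.** Four is right for the blood data: six received the medium dose and two withdrew. Section 4.1 openly gives two for MRI. The fault is that the objective applies one number to both.
- **That the 30-45mg/day range makes this a different dosage from the pilot's 45mg/day.** Section 5.1 labels the range as medium dose and titrates to the pilot's dose, with reductions for side effects. The range is stated openly and adds little to this point.

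It would also go too far to call the similarity question unanswerable throughout. For Nurr1 that depends on the treated SD, and at half the PPMI SD the nbM half-width is smaller than the pilot change.

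**Conclusion.** The concern holds as a mismatch between objective and analysis. The objective names the previous medium-dose patients as its benchmark; two of the four have MRI data; and nothing in Sections 5.1 or 19.1 estimates or tests similarity to them.

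On MRI, a direct comparison would be very imprecise. At the PPMI SDs the half-widths are 1.6 to 4.9 times the pilot changes. At half those SDs, pSN and DMN-T still exceed the pilot change and nbM does not. For Nurr1 the half-width runs from about 26 to 594 points over SDs of 22 to 500, so no firm statement is possible without the treated SD.

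These figures assume a common SD in new and pilot patients, one-year untreated SDs for the 24-week treated free-water changes, and no covariate adjustment. The mismatch itself rests on none of them. A formal equivalence test is not a workable remedy for MRI with two pilot patients.

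**What to change.** 1. In Sections 1.0 and 2.1, restate the objective as estimating the 24-week change in PBMC Nurr1 and in DMN-T, nbM and pSN free water in the 15 new patients, with 95% CIs, against the comparators named in Section 5.1.
2. State the pilot basis as four patients for blood and two for MRI.
3. In Section 19.1, replace the three-group randomized comparison text with the Section 5.1 comparisons.
4. Add one table showing new and pilot medium-dose changes and their difference with a 95% CI, labelled descriptive.
5. State that significance against controls or natural history will not be reported as similarity to the pilot.

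The cost is rewording in three sections, one extra table and a more modest stated objective. No additional patients or procedures are needed.

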### 2.0 Objectives\*

*2.1 Describe the purpose, specific aims, or objectives of this research.*

*Response: Determine if medium-dose lithium aspartate therapy in an additional 15 patients is associated with similar improvements in blood-based therapeutic*

targets and MRI-based biomarkers as observed in the previous four patients receiving this dosage.

2.2 State the hypotheses to be tested, if applicable.

*NOTE: A hypothesis is a specific, testable prediction about what you expect to happen in your study that corresponds with your above listed objectives.*

Response: Lithium therapy will engage one or more blood-based therapeutic targets and MRI-based disease-progression biomarkers implicated in PD pathophysiology.

